6.3.1 Premature termination criteria of entire clinical research

The sponsor should immediately discontinue the study when at least one of the following criteria is applicable:

When new information or other evaluation on the safety or efficacy of the study drug becomes
available that shows a change in the known risk/benefit profile of the concerned compound, and
risks/benefits are no longer tolerable for research subject participation in the study.

 When there is serious deviation from ethical guidelines or ICH-GCP that may threaten safety of the research subjects.

6.3.2 Criteria for premature termination of research implementing entities

A study site may be notified by the sponsor to discontinue clinical study if the site (including the principal investigator) is found in significant violation of Ethical Guideline for Clinical Research, protocol, or contractual agreement, is unable to ensure adequate performance of the study, or as otherwise permitted by the contractual agreement.

6.3.3 Procedures of clinical study suspension and premature termination of entire clinical study or study at a research implementing entity

In the event that the sponsor or a research implementing entity committee such as an ethics review committee decides to prematurely suspend or terminate the entire clinical study or clinical study at a research implementing entity, a study-specific procedure shall be provided by the sponsor. The procedure shall be followed by applicable research implementing entities during the course of clinical study suspension or premature termination.

6.4 Procedures for protocol revision

If the protocol needs to be revised, the sponsor shall consider and decide whether to revise the protocol.

The principal investigator of each research implementing entity shall be informed of the details of each protocol revision. Also, principal investigators shall confirm the content of the revision of the protocol and submit a letter of agreement to the sponsor as evidence of agreement with the protocol revision.

Upon notification, the principal investigator at each research implementing entity shall submit the revised contents to committees such as the IEC, as necessary according to institutional regulations for review, and obtain approval from the director of the entity.

7.0 SELECTION AND WITHDRAWAL CRITERIA OF RESEARCH SUBJECTS

7.1 Inclusion criteria

Research subjects shall fulfill all of the following criteria to be included in this clinical study:

- Research subjects who, in the opinion of the principal investigator or the investigator, are capable of understanding the content of the clinical research and complying with the research protocol requirements.
- 2. Patients who are able to sign and date the informed consent form and information sheet prior to the start of study procedures
- 3. Patients diagnosed with type 2 diabetes mellitus
- 4. Patients with an HbA1c (NGSP value) value \geq 6.5% and < 8.5% at the start of the observation period (Day -2)
- 5. Patients who experience a ≤ ±1.0% change in HbA1c (NGSP value) at the start of the observation period (Day -2) as compared with an HbA1c value obtained during the preceding 6 weeks
- 6. Patients receiving stable dietetic therapy and exercise therapy (if performed) for ≥ 4 weeks before the start of the observation period
- 7. Patients who in the opinion of the principal investigator or the investigator, does not have to change (including discontinuation or interruption) HMG-CoA reductase inhibitors or addition of new HMG-CoA reductase inhibitors during treatment period.
- 8. Men or women aged 20 years or older at the time of informed consent

[Rational for the inclusion criteria]

- 1.2. These were set as essential conditions for the clinical research.
- 3. Set as target disease for this study.
- 4. To evaluate the glycemic variation caused by the study drug accurately, the upper limit value was set at 8.5% (NGSP value) to exclude research subject with insufficient glycemic control.
- 5. To evaluate the glycemic variation accurately, the change variation of HbA1c was set to exclude research subject with unstable glycemic control
- 6. Set in consideration of the possibility of change in dietetic/exercise therapy may affect evaluation of glycemic variation.

- 7. This was set in consideration of the possibility that HMG-CoA reductase inhibitors may affect glycemic variation.
- 8. This was set to allow for separate assessment of men/women. The lower age limit was set to 20 years to allow patients to make a voluntary decision regarding their participation in this clinical research.

7.2 Exclusion criteria

Research subjects meeting any of the criteria below shall not be included in this research.

- 1. Patients who received anti-diabetic medications within 4 weeks prior to the start of the observation period.
- Patients who have changed (including discontinuation or interruption) HMG-CoA reductase
 inhibitors or received new HMG-CoA reductase inhibitors ≤ 4 weeks before the start of the
 observation period.
- 3. Patients with clinically evident hepatic dysfunction (e.g., AST or ALT \geq 2.5-fold the upper limit of normal at the start of the observation period [Day -2])
- 4. Patients with moderate renal dysfunction, severe renal dysfunction or renal failure (e.g., creatinine clearance < 50 mL/min or serum creatinine > 1.4 mg/dL in men or > 1.2 mg/dL in women [equivalent to the creatinine clearance for persons aged 60 years with a body weight of 65 kg] at the start of the observation period [Day -2])
- 5. Patients with severe heart disease, cerebrovascular disorder, or severe pancreatic, hematologic or other diseases
- 6. Patients with a history of gastric or small intestinal resection
- 7. Patients with proliferative diabetic retinopathy
- 8. Patients warranting insulin therapy for glycemic control (e.g., patients with severe ketosis, diabetic coma or precoma, type 1 diabetes mellitus, severe infection, perioperative patients, or serious trauma)
- 9. Patients with a history of hypersensitivity or allergy to DPP-4 inhibitors
- 10. Patients who experience an allergic reaction to metal during CGM at the start of the observation period (Day -2)
- 11. Patients with any malignant tumors
- 12. Habitual drinkers whose average daily alcohol consumption is > 100 mL^{Note 1)}

- 13. Patients who have any contraindications for the study drug or are taking any contraindicated concomitant drugs listed in the package insert
- 14. Patients anticipated to require any prohibited concomitant medications during the study period
- 15. Patients who are day and night lifestyle reversal
- 16. Patients participating in any other clinical studies at the time of informed consent for this study
- 17. Pregnant women, nursing mothers, women who are possible pregnant, or women who plan to become pregnant
- 18. Other patients who are considered inappropriate for participation in this study in the opinion of the principal investigator or investigator

Note 1: Alcohol conversion table (for reference)

Alcohol type	Variation	Alcohol strength (%)	Amount equivalent to alcohol 100 mL
	Sake	15%	670 mL (about 3 gos, 1 go=180 mL)
	Beer	5%	2,000 mL (about 3 large bottles)
	Happoshu		
Brewed alcohol	(low-malt beer -		
brewed account	like beverage)	5%	2,000 mL
	Wine	12%	830 mL
	Shaoxing rice		
	wine	18%	560 mL
	Shochu		
	(group ko)	35%	290 mL
	Shochu		
Spirits	(group otsu)	25%	400 mL
	Whisky	40%	250 mL (about 3 double glasses)
	Brandy	40%	250 mL (about 3 double glasses)
	Vodka	40%	250 mL (about 3 double glasses)
0 1: 1 1 1 1	Plum wine	13%	770 mL
Combined alcohol	Combined sake	16%	630 mL

[Rationale for the exclusion criteria]

- 1, 2. Set in order to evaluate drug efficacy accurately.
- 3, 5, 7, 10, 11, 13. These were set in consideration of safety of research subjects.
- 4. Severe renal dysfunction and renal failure shall be excluded because trelagliptin is contraindicated for these conditions. Moderate renal dysfunction shall be excluded in consideration of safety of research subjects.
- 6, 12, 14. Set in order to take in consideration of safety of research subjects and to evaluate drug efficacy accurately.
- 8, 9. Set as contraindication for trelagliptin and alogliptin treatment.
- 15..,16 Set in order to establish rational for evaluation of this study.
- 17. Set as safety of trelagliptin and alogliptin in pregnant women has not been established. Also, set as excretion of trelagliptin and alogliptin in breast milk was confirmed in non-clinical trials.
- 18. These were set as fundamental items for the research.

7.3 Prohibited concomitant drugs and restricted concomitant drugs

7.3.1 Prohibited concomitant drugs

The following drugs are prohibited from the start of observation period to end of treatment period.

- 1. Anti-diabetic medications other than the allocated oral hypoglycemic drug
- 2. Glucocorticoids (medications for local effect such as external preparations are excluded)
- 3. Estrogen preparations
- 4. HMG-CoA reductase inhibitors* other than those used at the time of informed consent *Dosage of HMG-CoA reductase inhibitors those used at the time of informed consent may not be changed.
- 5. Acetaminophen

[Rational for prohibited concomitant drugs]

1 to 5. Set as it may affect evaluation of drug efficacy.

7.3.2 Restricted concomitant drugs

The following drugs those used at the time of informed consent are permitted from the start of observation period to end of treatment period. However, change of dosage, addition of or change to a new drug for those drugs is prohibited unless the principal investigator and investigator consider necessary due to adverse events.

- 1. Lipid lowering agents other than HMG-CoA reductase inhibitors
- 2. Anti-hypertensive drug

7.4 Research Subject Management

The principal investigator and investigator shall instruct the research subject the items below.

- (1) Give instructions to take allocated oral hypoglycemic drug as directed. If poor compliance with study treatment (e.g., < 75% of the prescribed dose) after the previous visit has been found and does not improve, the research subject may be withdrawn from the research if appropriate for the circumstances.
- (2) If hypoglycemia symptom (hunger abnormal, feeling of weakness, trembling of hands and fingers, cold sweat, palpitations, etc.) is observed, take glucose or sucrose (sugar), and if it does not improve give instructions to visit promptly.
- (3) For dietetic therapy and exercise therapy (if performed), the principal investigator and investigator shall make sure prescriptions (instructions for calories, etc.) are consistent throughout the research period, and instruct the research subject to adhere to the dietetic therapy and exercise therapy (if performed).

- (4) When CGM is being conducted, the principal investigator and investigator shall instruct exercise therapy (if performed) that may be performed under the same conditions every day, and instruct the research subject to adhere to it.
- (5) When CGM is being conducted, give instruction to photograph every meal contents.
- (6) Instruct the research subject not to eat high-sugar, high-calorie food or beverage between meals during CGM.
- (7) When CGM is being conducted, give instructions to note necessary items into the research subject diary.
- (8) On visit days for planned laboratory tests, give instructions not to take oral hypoglycemic drug scheduled to be taken on that day. Further, at each visit, have the research subject report if drug has been taken or not the day before, and on the day of visit.
- (9) On visit days for planned laboratory tests, give instructions for fasting ≥ 10 hours before visit.
- (10) For research subjects of childbearing potential, give instructions to use adequate contraception. If pregnancy is discovered, have the research subject report promptly, and discontinue the research immediately.
- (11) The principal investigator and investigator shall instruct the research subject to adhere to instructed prohibited concomitant drugs. When drugs are taken other than the drugs prescribed by the principal investigator and investigator, have the research subject report its content.
- (12) Regarding subjective symptoms/objective findings, have the research subject report at visit the necessary items from its contents, onset date, degree, outcome and date of outcome.

7.5 Criteria for discontinuation or withdrawal of a research subject

The principal investigator or investigator shall record the main reason for discontinuation of protocol treatment on the case report form according to the classification described below. Refer section 9.1.12 for discontinuation case before randomization.

1. Adverse event

When the research subject had an adverse event that requires withdrawal of the research subject from the study because continued participation in the study would impose an unacceptable risk to the research subject's health, or when the research subject is unwilling to continue study participation because of the pretreatment event or adverse event.

2. Major protocol deviation

When it is discovered after randomization that a research subject does not meet the eligibility criteria or is not adhering to the protocol, and continued participation in the research would impose an unacceptable risk to the research subject's health.

3. Lost to follow-up

When the research subject failed to make visits and could not be contacted. The attempts that were made to contact the research subject shall be recorded in the source documents.

4. Voluntary termination

When the research subject wishes to withdraw from the research. The reason for discontinuation shall be recorded on the CRF when it is clarified.

5. Research termination

When the sponsor or a committee such as the IEC or regulatory authority has decided to terminate the study. Refer to Section 6.3.1 for details.

6. Pregnancy

When a female research subject is found to be pregnant.

Note: Research participation shall be immediately discontinued when pregnancy is known. Refer to Section 9.1.11 for procedure.

7. Others

Note: The specific reasons should be recorded on the CRF.

7.6 Procedures for discontinuation of individual research subjects

The principal investigator or investigator shall terminate a research subject's research participation when the research subject meets the criteria described in Section 7.5. Individual research subjects may discontinue their research participation without giving a reason at any time during the research. Should a research subject's participation be discontinued, the primary reason for termination shall be recorded on the CRF by the principal investigator or investigator. In addition, efforts shall be made to perform all tests/observations/evaluations scheduled at the time of discontinuation.

8.0 RESEARCH TREATMENT

This section indicates the treatment regimen of this clinical research. See the latest package insert for details and handling of each drug.

8.1 Treatment with the study drug

8.1.1 Study drug

(1) Study drug:

Generic name: Trelagliptin Succinate

Chemical name: 2- ({6- [(3R) -3-Aminopiperidin-1-yl] -3-methyl-2, 4-dioxo-3, 4-

dihydropyrimidin -1 (2H)-yl})methyl-4-fluorobenzonitrile monosuccinate

Generic name: Alogliptin benzonate

Chemical name:2- ({6- [(3R) -3-Aminopiperidin-1-yl]

-3-methyl-2,4-dioxo-3,4-dihydropyrimidin-1 (2H) -yl} methyl) benzonitrile monobenzoate

8.1.2 Dose and administration method

Trelagliptin 100 mg (once weekly) or alogliptin 25 mg (once daily) shall be administered orally before breakfast. However, the drug shall be administered as described below at the start of the treatment period (VISIT 2: Day 1) or during the treatment period (VISIT 3: Day 21).

At the start of the treatment period (VISIT 2: Day 1): The drug shall be administered after required tests/observations, etc.

During the treatment period (from VISIT 3 to VISIT 5):

Trelagliptin 100 mg/week group shall insert the sensor on a day between 3day and a day before Trelagliptin administration day. Trelagliptin 100 mg/week shall be administered before breakfast on the day of the drug administration. The next administration of Trelagliptin 100 mg is after the sensor removal.

Alogliptin 25 mg/day shall be administered after required tests/observations, etc at every VISIT without taking study drug. Research subjects shall take study drug prior to the every breakfast at home.

Duration of treatment shall be start of treatment period (Day 1) to end of treatment period (Day 29).

Dose and administration method for each administration group are shown in table 8.a.

Table8.a Administration group and administration method

Administration group	Dose	Route of administration:	Administration method
Trelagliptin group	Trelagliptin 100 mg	Oral	Once weekly, before
Tretagripuit group	Tretagnpun 100 mg	administration	breakfast
Alaslintin anaum	Alaalintin 25 ma	Oral	Once daily, before
Alogliptin group	Alogliptin 25 mg	administration	breakfast

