2.0 STUDY SUMMARY

Sponsor:	Study drug:
Takeda Pharmaceutical Company Limited	Trelagliptin
	Alogliptin

Study title:

An exploratory study of the effects of trelagliptin and alogliptin on glycemic variation in patients with type 2 diabetes mellitus

Protocol number: Trelagliptin-4001 (122/NRP-001)

Clinical study design:

This is a multi-center, randomized, open-label, parallel-group comparative, exploratory study to evaluate the effect of trelagliptin administered at a dose of 100 mg once weekly or alogliptin administered at a dose of 25 mg once daily for 4 weeks on glycemic variation in patients with type 2 diabetes mellitus using continuous glucose monitoring (CGM).

After informed consent, patients determined to be eligible for this study based on the eligibility assessment will be randomized to either the trelagliptin 100 mg group or the alogliptin 25 mg group (at a ratio of 1:1), using "HbA1c at the start of the observation period (< 7.5% or $\ge 7.5\%$)" and age (< 65 or ≥ 65) as a stratification factor for randomization.

The total duration of evaluation will be 31 days, consisting of the observation period for 2 days and a treatment period for 29 days (4 weeks). CGM will be performed on research subjects on an outpatient basis (in 2 assessments) for 2 days from the start of the observation period (Day -2) and for 9 days from Day 21 of the treatment period.

Objective:

To evaluate the effect of trelagliptin administered orally at a dose of 100 mg once weekly or alogliptin administered orally at a dose of 25 mg once daily for 4 weeks on glycemic variation in an exploratory manner and as preliminary to examine the influence of the once-weekly administration and blood glucose fluctuations due to the difference in the daily administration in patients with type 2 diabetes mellitus

Study population:

Patients with type 2 diabetes mellitus

Planned number of research subjects:	Number of study research		
The planned minimum number of research subjects evaluable	implementing entities:		
for the primary endpoint in each group is as follows:	3 medical institutions		
Trelagliptin 100 mg group: 15			
Alogliptin 25 mg group: 15			

Total: 30	
Dans and mathed of administrations	Donto of administration.
Dose and method of administration:	Route of administration:
Trelagliptin 100 mg once weekly or alogliptin 25 mg once	Oral
daily, taken orally before breakfast	
Duration of treatment:	Duration of evaluation:
4 weeks	31 days (observation period for 2 days

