9.1.9 Continuous glucose monitoring (CGM)

Conducted according to Schedule of Research Procedures (Appendix A) Details shall be specified separately in the operation procedures manual.

- (1) Device used in this study
 - , leased from the sponsor.
- (2) Self-measurement of blood glucose (SMBG)

Use device leased from sponsor

Research subjects shall measure blood glucose levels every day during CGM in the observation and treatment periods. At least, blood glucose levels shall be measured at three time points on the first day of CGM ([1] at least 2 hours after the recorder is connected and [2] 2 hours after the first is measured. [3] at bedtime) and at four time points from the second day onward ([1] before breakfast, (2) before lunch, (3) before evening meal, and (4) at bedtime).

The glucose levels from SMBG shall be used for correction of glucose levels obtained from CGM.

(3) Observation period

A sensor shall be inserted at the start of the observation period (Day -2) and removed at the start of treatment (Day 1)

(4) Treatment period

A sensor shall be inserted (VISIT 3: Day 21), exchanged (VISIT 4: Days 24 to 26), and removed (VISIT 5: Day 29) during the treatment period.

(5) Dietetic therapy and exercise therapy

Research subjects shall present photographs of all meals to the principal investigator or investigator during CGM. Also, the meal provided by the sponsor shall be taken according to the calories prescribed by the sponsor for each research subject at the meal times shown below.

Time point of provision of meals: evening meal at start of observation period (Day-2), evening meal on first and seventh of CGM to be performed from Day 21 for 9 days.

Research subjects shall only conduct exercise therapy feasible (if performed) under the same conditions every day during CGM.

The principal investigator or investigator shall prescribe consistent dietetic therapy and exercise therapy (if performed) throughout the research period. Compliance with dietetic therapy and exercise therapy(if performed) shall be investigated and rated on a four-point scale as follows:

- 1. Compliant (compliance rate $\geq 90\%$)
- 2. Almost compliant (compliance rate $\geq 70\%$)
- 3. Generally compliant (compliance rate $\geq 50\%$)
- 4. Minimally compliant (compliance rate < 50%)

(6) Research subject diary

Research subjects shall complete the subject diary every day during CGM and submit the diary to the principal investigator or investigator.

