9.3.4 Treatment period (Visit 4: Day 24)

The test, observation, and endpoints to be implemented during the treatment period (Visit 4: Day 24) are shown below.

- Physical examination
- Concomitant drugs
- Laboratory tests Drug-taking status
- Compliance with dietetic therapy and exercise therapy
- CGM (exchange sensor)
- Self-measurement of blood glucose (self-measured by research subject)
- Adverse event

9.3.5 At end of treatment period (Visit 5: Day 29) or discontinuation during treatment period

The test, observation, and evaluation items to be implemented during at the end of treatment period (Visit 5: Day 29) are shown below.

- Physical examination
- Body weight
- Concomitant drugs
- Laboratory tests
- Drug-taking status
- Compliance with dietetic therapy and exercise therapy
- CGM (remove sensor)
- Self-measurement of blood glucose (self-measured by research subject until removal of CGM sensor)

Adverse event

The test, observation, and endpoints to be implemented at discontinuation of treatment period are shown below.

- Physical examination
- Body weight
- Concomitant drugs
- Laboratory tests
- Drug-taking status
- Compliance with dietetic therapy and exercise therapy
- Adverse event
- Reason of discontinuation

The status of all randomized research subjects at the end of the clinical research shall be recorded on the CRF.

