Appendix A Schedule of Research Procedures

		Observation period Treatment period						
Time of Visit	Week			0			4	Disconti nuation ^{(g}
	Day	-14	-2	1 ^(b)	21 ^(c)	24 ^(c)	29 ^(c)	-
Allowable ran	nge (Day)	-28 to -2	-4 to -2	1	19 to 35	24~39 ^(f)	29 to 43	-
VISIT Numb	er		1	2	3	4	5	-
Informed procedure	consent	×						
Inclusion/Exc criteria		×	×					
Demographic information		×						
Medical pre-treatment		×	×					
Physical exan		×	×	(\times)	×	×	×	×
Body weight,	BMI		×		×		×	X
Height		×						
Concomitant		×	×	(\times)	×	×	×	×
Concurrent di		×	×					
Laboratory te	sts ^(a)		×		×	×	×	×
HbA1c			×					
Drug -taking					×	×	×	X
Prescription of dietetic therapy and exercise therapy and assessment of compliance		×	×	(×)	×	×	×	×
CGM	-		× (d) (Sensor	(d) × (Sensor	× (d) (Sensor	× (d) (Exchange sensor)	(d) × (Sensor	
Self-measurer			insertion) × (e)	remove) × (e)	× (e)	× (e)	remove) × (e)	
Adverse even monitoring	t			×				

(a) Measured on VISIT1 (Day-2), and the first and ninth days of the 9-day CGM starting on Day 21

Blood tests: glycoalbumin, 1,5-AG, fasting insulin, fasting glucagon, fasting proinsulin, fasting GLP-1, fasting GIP*, DPP-4 activity Measured on 1 point during fourth and sixth day of the 9-day CGM starting on Day 21

Blood tests: fasting GLP-1, fasting GIP, DPP-4 activity

- (b) The starting day of study treatment in the treatment period is designated as Day 1. The study drug shall be administered after required tests/observations, etc. The day before the start of study treatment in the treatment period is designated as Day -1. It is performed at the visit when principal investigator or investigator consider as needed.
- (c) Trelagliptin 100 mg/week group shall insert the sensor on a day between 3 day and a day before Trelagliptin administration day. Trelagliptin 100 mg/week shall be administered before breakfast on the day of the drug administration.

Alogliptin 25 mg/day shall be administered after required tests/observations, etc at every VISIT without taking study drug. Research subjects shall take study drug prior to the every breakfast at home.

- (d) To be performed by study site personnel
- (e) At least, blood glucose levels shall be measured at three time points on the first day of CGM ([1] at least 2 hours after the recorder is connected and [2] 2 hours after the first is measured. [3] at bedtime) and at four time points from the second day onward ([1] before breakfast, (2) before lunch, (3) before evening meal, and (4) at bedtime).

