- (f) Research subjects should visit the study site on a day between fourth and sixth day of the 9-day CGM starting on Day 21.
- (g) To be performed to the extent possible

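### In the trelagliptin arm, a 2- or 3-day sensor lead does not fit a 9-day CGM with ninth-day tests; a site that stops on that day can miss the last one or two post-dose windows

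*Protocol*

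**What the plan says.** All protocol references are to the current version, which comes first in the file.

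- **Insertion.** Section 8.1.2 states: "Trelagliptin 100 mg/week group shall insert the sensor on a day between 3day and a day before Trelagliptin administration day". Appendix A note (c) repeats this, and the Visit 3 range is Day 19 to 35. The same section adds: "The next administration of Trelagliptin 100 mg is after the sensor removal".
- **CGM length.** Section 2.0 has CGM running "for 2 days from the start of the observation period (Day -2) and for 9 days from Day 21 of the treatment period".
- **Tests.** Appendix A note (a) has the laboratory tests "Measured on VISIT1 (Day-2), and the first and ninth days of the 9-day CGM starting on Day 21". Section 13.1.3 also names the ninth CGM day as an evaluation point.
- **Exchange and removal.** Section 9.1.9(4) has the sensor "exchanged (VISIT 4: Days 24 to 26), and removed (VISIT 5: Day 29) during the treatment period". Note (f) places Visit 4 on the fourth to sixth CGM day. The Visit 5 range is Day 29 to 43, and 9.3.5 puts laboratory tests and sensor removal at that same visit.
- **Provided meals.** In the treatment period, 9.1.9(5) gives "evening meal on first and seventh of CGM to be performed from Day 21 for 9 days".
- **SAP.** Section 2 starts the first treatment window 4 hours before breakfast on the dose day after insertion. It labels the seven windows as the 2nd to 8th CGM day. Its reference days for the Day 9 laboratory tests are 29, 36 and 43, for Visit 3 on Days 19–25, 26–32 and 33–35. Section 10.2 covers only laboratory values below the determination limit.

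**The concern.** The lead can vary, but the length of CGM and the day of the end tests are counted from insertion. Each extra day of lead therefore moves the ninth CGM day one day closer to the dose. The tests belong to the ninth CGM day and share a visit with sensor removal, so a site following note (a) has a reason to end CGM then.

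Any windows lost would be the last of the weekly dosing interval, which matter most for describing a once-weekly drug. They are daily time points of the primary endpoint. The daily mean in each arm with its 95% CI is the first analysis listed in 13.1.3, so the loss would affect the primary objective and not only the secondary between-arm comparison.

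**Working it through.** **Inputs.** Lead k = 1, 2 or 3 days (8.1.2). Weekly doses from Day 1, so the candidate dose days D are 22, 29 and 36. Visit 3 range 19–35 and Visit 5 range 29–43 (Appendix A). Seven windows (SAP 7.1), read as contiguous 24-hour periods that start 4 hours before breakfast on D to D+6. Visits with laboratory tests are fasting visits (7.4), so I take removal to be in the morning. A window is then complete only if the sensor is still in place the next morning.

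**Formulas.**
- Insertion = D − k.
- Ninth CGM day = D − k + 8.
- Complete windows by the ninth CGM day = 8 − k.
- Days from dose to ninth-day tests = 8 − k.
- Removal on D+7 is CGM day k + 8.
- The seventh-CGM-day meal falls on D + 6 − k, which is post-dose day 7 − k (dose day = 1).

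**The plan's own figure.** D = 22 and k = 1 give insertion on Day 21, ninth CGM day on Day 29, and 7 of 7 windows. The 9-day design reproduces exactly for this lead.

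| Dose day | Lead | Insertion | Ninth CGM day | In Visit 5 range | Complete windows if CGM stops then | SAP reference day (= D+7) |
|---|---|---|---|---|---|---|
| 22 | 1 | 21 | 29 | yes | 7 | 29 |
| 22 | 2 | 20 | 28 | no | 6 | 29 |
| 22 | 3 | 19 | 27 | no | 5 | 29 |
| 29 | 1 | 28 | 36 | yes | 7 | 36 |
| 29 | 2 | 27 | 35 | yes | 6 | 36 |
| 29 | 3 | 26 | 34 | yes | 5 | 36 |
| 36 | 1 | 35 | 43 | yes | 7 | 43 |
| 36 | 2 | 34 | 42 | yes | 6 | 43 |
| 36 | 3 | 33 | 41 | yes | 5 | 43 |

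For a Day 22 dose with a 2- or 3-day lead, the Visit 5 lower bound holds removal until Day 29. All seven windows are kept, but CGM then lasts 10 or 11 days. For the later doses nothing in the ranges prevents a ninth-day stop.

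**Tests and meals.** For leads of 1, 2 and 3 days, ninth-day tests fall 7, 6 and 5 days after the dose. The seventh-CGM-day meal falls on post-dose day 6, 5 and 4.

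**Alogliptin.** With the first window on CGM day 2, the seventh window is complete on the morning of CGM day 9, so 7 of 7 are kept.

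**Illustrative precision.** The number of affected subjects is unknown. Suppose 15, 12 or 10 trelagliptin subjects have the last window. The 95% CI half-width in SD units is t(0.975, n−1)/√n within the arm, and t(0.975, n+13)·√(1/n + 1/15) against 15 alogliptin subjects.

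| n | Trelagliptin mean | Difference between arms |
|---|---|---|
| 15 | 0.554 | 0.748 |
| 12 | 0.635 (+15%) | 0.798 (+7%) |
| 10 | 0.715 (+29%) | 0.845 (+13%) |

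**The case against.** The strongest reply is that the ninth day is a nominal label. Counted from Day 21 it is Day 29, which is Visit 5. Section 9.1.9 ties removal to Visit 5, section 8.1.2 lets the sensor stay until the next dose, and the SAP reference days equal dose day + 7 for every permitted lead. On that reading no window is lost and the tests do not shift. The operations manual, which was not available, may say so. This stands as far as it goes: no passage orders removal on the ninth CGM day. It does not reconcile the text, because removal on dose day + 7 makes CGM last 10 or 11 days after a longer lead. The protocol nowhere allows for that, and note (a) still names the ninth day.

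Three further replies have force.

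- Alogliptin at visits is taken after the required procedures. Its first dose after insertion could therefore fall on the insertion day, with a window that opens before the sensor is in place. That alogliptin loses nothing therefore rests on the SAP label of CGM day 2.
- The precision figures use assumed counts and apply only to the last day's estimate.
- SAP 7.1 analyses each day separately, so an absent window simply drops out. The gap is in partial windows, which could enter a daily SD, and in the 7-day means of 7.2(2).

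The SAP's window wording is also unclear. The second window starts at the end of Day 2, while the dose day is numbered Day 1. Read literally, this skips a day and leaves 6, 5 or 4 complete windows by the ninth CGM day. Read as CGM day 2, the windows are contiguous, as assumed above. The extra loss per day of lead is the same either way.

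**Conclusion.** The conflict is real and lies within the current protocol, and between it and the SAP. It applies to leads of 2 or 3 days in the trelagliptin arm. A one-day lead fits and loses nothing. For a Day 22 dose the rules cannot all be met, but no data are lost if the sensor comes out on Day 29. For a Day 29 or 36 dose, a ninth-day stop would lose 1 of 7 windows with a 2-day lead and 2 of 7 with a 3-day lead.

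A reader might infer that data loss is built into the design, that every later-cycle dose is affected, or that loss confined to one arm is established. The documents support none of these. Removal on dose day + 7 is allowed, a one-day lead is always safe, and the alogliptin result depends on where its first window starts.

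The trial is exploratory and its size is not based on power, so this does not undermine it. It should still be corrected, because daily time points of the primary endpoint are exposed and the remedy is cheap. The arithmetic is firm. How often the loss would occur is unknown.

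**What to change.** Reconcile protocol 2.0, 8.1.2, 9.1.9, 13.1.3 and Appendix A notes (a), (c) and (f) with SAP section 2.

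- **Trelagliptin.** End CGM and hold the Visit 5 tests when seven 24-hour windows from the dose day after insertion are complete (Day 29, 36 or 43), instead of on the ninth CGM day. These days lie in the Visit 5 range, equal the SAP reference days, and respect the rule that the next dose follows removal. Place the two provided treatment-period meals by the same count; a one-day lead puts them on the evening before the dose and on post-dose day 6.
- **Alogliptin.** Keep the 9-day CGM with the first window on the day after insertion (CGM day 2), and say so in the SAP. Counting from the first dose after insertion would not work here: a dose on a Day 21 insertion day would end CGM on Day 28, its eighth day and before the Visit 5 range. The ninth day reaches that range only for insertion on Day 21 or later (21 + 8 = 29), so state how the Day 19 lower bound of Visit 3 applies to this arm.
- **SAP.** Label the windows 1 to 7 with an arm-specific anchor. In 10.2, treat an incomplete CGM window as missing, and flag 7-day means based on fewer than seven windows.

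The cost is wording, plus up to two extra CGM days with self-measured glucose and diary entries for early trelagliptin insertions. Sensor exchange also becomes tighter. If no sensor is worn longer than 5 days, the most the 9-day plan implies, exchange must fall on CGM day k + 3 to 6: days 5–6 for a 2-day lead and day 6 for a 3-day lead. For a Day 22 dose the Visit 4 range from Day 24 already imposes this. The device wear limit must be confirmed; if it does not allow longer CGM, reconcile the insertion lead with the 9-day CGM instead. Dosing is unchanged.
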